7.5.6. Management of Bone Abnormalities

Among Group 1 subjects, if bone abnormalities are detected or suspected in paediatric patients, consultation with an endocrinologist and/or nephrologist should be obtained. Group 2 subjects with detected or suspected bone abnormalities should be managed as per the local standard of care.

7.5.7. Management of ALT Flares

Flares on treatment: Spontaneous exacerbations in CHB are relatively common and are characterised by transient increases in serum ALT. After initiating antiviral therapy, serum ALT may increase in some patients. In patients with compensated liver disease, these increases in serum ALT are generally not accompanied by an increase in serum bilirubin concentrations or hepatic decompensation. Patients with cirrhosis may be at a higher risk for hepatic decompensation following hepatitis exacerbation, and therefore should be monitored closely during therapy.

Flares after treatment discontinuation: Acute exacerbation of hepatitis has also been reported in patients who have discontinued HBV therapy. Post-treatment exacerbations are usually associated with rising HBV DNA, and the majority appears to be self-limited. However, severe exacerbations, including fatalities, have been reported. Hepatic function should be monitored at repeated intervals with both clinical and laboratory follow-up for at least 6 months after

discontinuation of HBV therapy. If appropriate, resumption of HBV therapy may be warranted. In patients with advanced liver disease or cirrhosis, treatment discontinuation is not recommended since post-treatment exacerbation of hepatitis may lead to hepatic decompensation. Patients should be placed on commercially available HBV therapy following study drug discontinuation. Liver flares are especially serious, and sometimes fatal in patients with decompensated liver disease.

On-Treatment ALT Flare and Post-Treatment Exacerbation of Hepatitis are defined as:

- Serum ALT $> 2 \times$ baseline and $> 10 \times$ ULN, with or without associated symptoms OR
- Confirmed ALT elevation (defined as 1-grade shift or $2 \times$ previous value) associated with confirmed changes outside of the normal range in other laboratory parameters suggestive of worsening hepatic function (total bilirubin ≥ 2 mg/dL above baseline, abnormal PT ≥ 2 seconds or INR ≥ 0.5 over baseline, abnormal serum albumin ≥ 1 g/dL below baseline or elevated serum lactate levels (if available), defined as $2 \times$ ULN per the Adult AIDS Clinical Trials Group (AACTG) guidelines).

7.5.7.1. Management of ALT Flare in Subjects Receiving Tenofovir DF

If laboratory results indicate (1) elevation of ALT $> 2 \times$ baseline and $> 10 \times$ ULN OR (2) abnormal laboratory parameters suggestive of worsening hepatic function (abnormal bilirubin ≥ 2 mg/dL above baseline, abnormal PT ≥ 2 sec above baseline, INR ≥ 0.5 above baseline, abnormal albumin ≥ 1 g/dL decrease from baseline or elevated serum lactate levels $> 2 \times$ ULN along with any ALT elevation (i.e., grade shift or $2 \times$ previous value), the following is recommended:

- Schedule the subject to return to the clinic as soon as possible and ideally no later than one week after the initial labs were drawn. During the visit, perform a clinical assessment of the subject. The assessment should include a physical examination and evaluation of the subject's mental status.
- Draw blood samples, request lactate testing and send for confirmation of elevated serum transaminases (ALT/AST), total bilirubin and PT/INR, and albumin. [Note: If, in the investigator's judgment, the central laboratory cannot provide adequate turn around time, the confirmation test may also be performed at a local laboratory. However, the central laboratory results are considered definitive].

If the elevations are confirmed, request the central clinical laboratory to conduct reflex testing for serum HBV DNA, HBV serology (HBeAg, HBeAb, and HBsAg), HDV, HAV IgM, and HCV serology.

Based on the results of the confirmatory tests, the following treatment modifications are recommended:

Elevated Liver Enzymes, Normal Bilirubin, Normal PT/INT, Normal Albumin, Normal Lactate

If ALT and/or AST levels are elevated (i.e., $> 2 \times$ baseline and $> 10 \times$ ULN) but total bilirubin and PT/INR, albumin and lactate are normal, the subject may remain on Tenofovir DF and should be monitored every week until ALT/AST return to normal or baseline levels. During monitoring:

- If ALT/AST levels decline within 4 weeks, the subject should remain on study and return to the clinic per protocol.
- If after 4 weeks of monitoring, ALT/AST values remain elevated (e.g., $> 2 \times$ baseline and $> 10 \times$ ULN) or have worsened, with bilirubin $\leq 2.5 \times$ ULN, PT $\leq 1.5 \times$ ULN, or abnormal albumin or lactate levels, the investigator should consult with the Gilead Medical Monitor.
- If ALT remains $> 2 \times$ baseline and $> 10 \times$ ULN and the bilirubin or PT values are confirmed at $> 2.5 \times$ ULN or $> 1.5 \times$ ULN, respectively, the investigator should consider discontinuing Tenofovir DF and initiating alternative HBV therapy (see below). However, prior to initiating alternative therapy, medical management of the subject should be discussed with the Gilead Medical Monitor. (Note: Once a subject has started alternative therapy, s/he must be discontinued from the study.)

Elevated Liver Enzymes, Elevated Bilirubin and PT/INR ($>$ Grade 2) Symptomatic Elevated Lactate ($> 2 \times$ ULN) or Asymptomatic Elevated Lactate ($> 4 \times$ ULN)

If ALT/AST values are elevated (i.e., $> 2 \times$ baseline and $> 10 \times$ ULN) and bilirubin or PT values are confirmed at $> 2.5 \times$ ULN or $> 1.5 \times$ ULN, respectively, or lactate levels are increased (symptomatic and $> 2 \times$ ULN or asymptomatic and $> 4 \times$ ULN) the investigator should consider discontinuing Tenofovir DF and initiating alternative HBV treatment. The subject must be monitored weekly for as long as enzyme levels and bilirubin and PT/INR remain elevated or above baseline values. Refer to [Appendix 6](#)

for specific guidelines for the management of symptomatic and asymptomatic hyperlactatemia.

- If the ALT/AST levels return to the baseline level and/or Grade 2 or lower during the first 8 weeks of monitoring, Tenofovir DF may be resumed.
- If the ALT/AST levels, bilirubin, PT/INR or lactate levels remain elevated up through Week 8 or deteriorate at any point, the investigator should consult with the Gilead Medical Monitor.

7.5.7.2. Management of Exacerbation of Hepatitis in Subjects Who Have Discontinued Study Medication (Tenofovir DF)

If laboratory results indicate (1) an ALT elevation $> 2 \times$ baseline and $> 10 \times$ ULN OR (2) abnormal laboratory parameters suggestive of worsening hepatic function (bilirubin ≥ 2 mg/dL above baseline, abnormal PT ≥ 2 secs above baseline, abnormal albumin ≥ 1 g/dL below baseline or elevated lactate levels $> 2 \times$ ULN) along with any ALT elevation (i.e., 1 grade shift or $2 \times$ previous value) and the subject is on no post-study therapy for HBV, the following is recommended:

- Schedule the subject to return to the clinic as soon as possible and ideally no later than 1 week after the initial labs were drawn. During the visit, perform a clinical assessment of the subject. The assessment should include a physical examination and evaluation of the subject's mental status.
- Draw blood samples and request lactate testing and confirmation of elevated serum transaminases (ALT/AST), bilirubin, PT/INR, and albumin. [Note: If, in the investigator's judgment, the central lab cannot provide adequate turn around time, the confirmation test may also be performed at a local lab. However, the central lab results are considered definitive].
- If the elevations are confirmed (e.g., ALT $> 2 \times$ baseline and $> 10 \times$ ULN) OR (2) abnormal laboratory parameters suggestive of worsening hepatic function (abnormal bilirubin ≥ 2 mg/dL above baseline, abnormal PT ≥ 2 secs above baseline, abnormal albumin ≥ 1 g/dL below baseline, or elevated lactate levels $> 2 \times$ ULN) along with any ALT elevation (i.e., 1 grade shift or $2 \times$ previous value), request the clinical laboratory to conduct reflex testing for serum HBV DNA, HBV serology (HBeAg, HBeAb, and HBsAg), HDV, HAV IgM and HCV. If serum HBV DNA is increasing, the investigator should consider immediate initiation of approved therapy.

The subject should be followed until the abnormal ALT/AST values, bilirubin, PT/INR, albumin or lactate laboratory parameters return to normal or baseline up to a maximum of 6 months after the initial occurrence of the event. Refer to [Appendix 6](#)

for specific guidelines for the management of symptomatic and asymptomatic hyperlactatemia.

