Screening measures for Monitoring Groups 1 and 2 will include determining a subject's eligibility into the study with the following criteria: current age, documentation of chronic HBV infection, prior Tenofovir DF exposure, weight, laboratory assessments, ability to swallow solid tablets, subject's ability to adhere to treatment regimen, obtaining written informed consent from subject's parent or legal guardian or obtain informed assent from the subject

Baseline measures for Monitoring Groups 1 and 2 will include laboratory assessments for HBV DNA, HBV serology, HCV, HDV, and HIV polymerase chain reaction (PCR) testing, HBV genotyping, serum renal and bone chemistries, liver function, hematology, urinalysis. DEXA imaging, a physical exam (including pregnancy testing for females), current concomitant medications and any reported prior bone and renal AEs, will also be collected.

FREQUENCY OF STUDY PROCEDURES ([Appendix 2](#)):

Subjects enrolled to either Group 1 or 2 will have the following measures assessed:

- HBV DNA: every 12 weeks
- HBV serology: every 24 weeks
- Liver chemistry (i.e., alanine aminotransferase (ALT), alkaline phosphatase (ALP), aspartate aminotransferase (AST), total and direct bilirubin, total protein, albumin, gamma glutamyl transpeptidase (GGT), lactate dehydrogenase (LDH), creatine kinase (CK) every 24 weeks
- Hematology (i.e., complete blood count with differential and platelets, PT/INR): every 24 weeks
- Physical Examination and Drug Dispensing: every 12 weeks
- Documentation of bone or renal AEs since the subject's last visit
- Documentation of medical management in the event of bone or renal AEs

Subjects enrolled to Group 1 will have the following additional monitoring;

- DEXA: every 24 weeks from Baseline to Week 96 (5 scans)
- Serum bone chemistry (i.e., calcium, phosphorus, vitamin D levels (25-hydroxy and 1, 25 dihydroxyvitamin), parathyroid hormone (PTH), osteocalcin, bone-specific alkaline phosphatase, N and C telopeptides): every 24 weeks
- Serum renal chemistry (i.e., glucose, creatinine, calculated creatinine clearance, magnesium, bicarbonate, chloride, potassium, sodium): at 4 weeks and 12 weeks from Baseline and every 12 weeks thereafter, according to SmPC
- Urinalysis (i.e., protein, glucose, creatinine, phosphate, bicarbonate, blood, calcium): at 4 weeks and 12 weeks from Baseline and every 12 weeks thereafter

Subjects enrolled to Group 2 will have the following monitoring:

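### Protocol 7.5.7.1 (ALT flare on treatment) gives inconsistent rules for ending weekly checks and for resuming drug, and has no treatment branch for flares that meet only its second trigger

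*Protocol*

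**What the plan says.** Protocol 7.5.7.1 opens with two alternative triggers. The first is ALT above 2 × baseline and above 10 × ULN. The second is a laboratory sign of worsening hepatic function "along with any ALT elevation (i.e., grade shift or" twice the previous value). Either one leads to recall, clinical assessment, a confirmatory draw and, if confirmed, reflex testing. Then: "Based on the results of the confirmatory tests, the following treatment modifications are recommended". Two branches follow.

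- **Normal bilirubin, PT/INR, albumin and lactate.** Entry needs ALT and/or AST above 2 × baseline and above 10 × ULN. The subject may stay on drug and "should be monitored every week until ALT/AST return to normal or baseline levels". The first bullet reads "If ALT/AST levels decline within 4 weeks, the subject should remain on study and return to the clinic per protocol". The second sends values still elevated or worse after 4 weeks to the Medical Monitor.
- **Raised bilirubin, PT or lactate.** Entry needs the same ALT/AST condition plus bilirubin above 2.5 × ULN, PT above 1.5 × ULN, or raised lactate. The investigator should consider stopping drug. "The subject must be monitored weekly for as long as enzyme levels and bilirubin and PT/INR remain elevated or above baseline values". Drug may be resumed "If the ALT/AST levels return to the baseline level and/or Grade 2 or lower during the first 8 weeks of monitoring". The last bullet asks for a Medical Monitor consultation if ALT/AST, bilirubin, PT/INR or lactate stays elevated through Week 8 or deteriorates at any point.

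Outside this section, Protocol 7.5 speaks of restarting after the event has resolved. Protocol 7.5.2 withholds drug for a confirmed, related Grade 3 abnormality until it is Grade 2 or lower, and 7.5.3 stops drug permanently for a related Grade 4. The liver chemistry item in Protocol 3.2 ends "creatine kinase (CK) every 24 weeks". Appendix 2 puts these tests at Weeks 24, 48, 72 and 96. Sections 6.4.2 and 6.4.5 list none at Weeks 12, 36, 60 or 84.

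**The concern.** A site managing a flare needs to know when the extra checks end, what must have recovered before drug may restart, and which branch the subject is in. In the first branch, one sentence ties the end of weekly checks to a level and the next ties it to a direction of change. In the second, bilirubin, PT or lactate helps put the subject in the branch, but the resume bullet does not look at them. The entry conditions of both branches are narrower than the section's triggers. Two sites could follow the text faithfully and treat the same open-label adolescent differently. What is at stake is safety follow-up and the consistency of flare management.

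**Working it through.** No figure in the plan is being reproduced. The check sets the rules side by side and runs example results through them. The ALT and bilirubin values are illustrative.

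**(a) Normal-bilirubin branch.** Assume baseline 3 × ULN and a peak of 14 × ULN. Weekly checks continue while ALT is above baseline (above 3). The decline bullet is met by any value below 14. The consultation bullet's own example is met when ALT is above 2 × 3 = 6 and above 10.

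| ALT now (× ULN) | Weekly checks continue | Decline bullet met | Consultation example met after 4 weeks |
|---|---|---|---|
| 13 | yes | yes | yes |
| 11 | yes | yes | yes |
| 8 | yes | yes | no |
| 4 | yes | yes | no |
| 3 | no | yes | no |

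The weekly sentence and the decline bullet agree only once ALT is back at baseline. At every value in between, one continues weekly checks and the other returns the subject to scheduled visits.

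Timing, for a flare found at the Week 24 visit:
- Recall is ideally within 1 week, so the confirmatory draw is at about Week 25. Branch entry follows from that result.
- Suppose a decline is then seen at Week 26, 27 or 28.
- Under the weekly sentence, the next ALT is 1 week later.
- Under the decline bullet, the next scheduled liver chemistry is Week 48: 48 − 26 = 22 weeks, 48 − 27 = 21 weeks, 48 − 28 = 20 weeks.

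**(b) Raised-bilirubin/PT branch.** Take ALT down to 4 × ULN, which is Grade 2 (Appendix 4: above 2.50 to 5.00 × ULN), with bilirubin still 3 × ULN, which is Grade 3 (above 2.5 to 5.0 × ULN).
- The resume bullet is met.
- The weekly-monitoring sentence still treats the event as open.
- At Week 8 the consultation bullet is also met.
- If the bilirubin is judged clinically significant and drug-related, and is confirmed, 7.5.2 says to withhold drug.
- Before Week 8, if nothing deteriorates, no sentence within the branch links resumption to bilirubin, PT/INR or lactate.

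**(c) Coverage of the triggers.** The documents give no bilirubin ULN; 1.0 to 1.2 mg/dL is assumed.
- ALT 6 × ULN, baseline and previous value 2 × ULN, bilirubin 3.2 mg/dL from 0.6. The first trigger fails (6 is not above 10). The second is met: the bilirubin rise is 3.2 − 0.6 = 2.6, at least 2 mg/dL, and 6 is at least 2 × 2. No branch applies.
- ALT 12 × ULN, baseline 7 and previous value 4 × ULN, bilirubin 3.6 from 0.6. The first trigger fails (12 is not above 2 × 7 = 14). The second is met (rise 3.0; 12 is at least 2 × 4). No branch applies.

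Both results hold at either assumed ULN, because both branches need the ALT/AST condition of the first trigger. Yet worsening function with a lesser ALT rise is part of the protocol's own flare definition in 7.5.7.

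**The case against.** The strongest reply is that 7.5.7.1 should not be read alone, and much of that stands.

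- **Drug restart.** A reader might infer that drug can be restarted on ALT alone whatever bilirubin or PT is doing. The documents do not support that. The branch's entry levels for bilirubin and PT begin at Grade 3 in Appendix 4, so 7.5.2 and 7.5.3 separately hold or stop drug when the abnormality is related, and 7.5 links restart to resolution. The resume wording is also permissive. What remains is that the resume bullet does not match those rules or its own Week 8 bullet.
- **Three-way conflict.** A fall that leaves ALT above 10 × ULN meets three instructions at 4 weeks, and a reader might call this a three-way conflict. Weekly checks and a consultation are compatible. The conflict is between weekly checks and return to scheduled visits.
- **Meaning of the decline bullet.** Decline could be read as decline to baseline, or the per-protocol visits as including the weekly ones. The text says neither.
- **A longer gap.** Counting from Week 25 would lengthen the gap. That draw is likely to be the confirmatory one, which precedes branch entry. A clinic visit with physical examination and HBV DNA also falls at Week 36, though without scheduled liver chemistry.
- **Flare counts.** A reader might infer that the SAP's flare incidence is at risk. SAP 7.2.2.3 counts a flare from the triggering or confirmed result, so later follow-up does not remove one already counted.
- **Second-trigger subjects.** They are not unmanaged. Recall, assessment, confirmation, reflex testing, the grade rules and the Medical Monitor remain.
- **Timing of the change.** SAP 1.4 and 2.1 record closure with 30 subjects enrolled and a last visit in April 2018. A clarification can no longer govern a subject in this study. That limits its practical reach but does not make the text consistent.

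**Conclusion.** The point holds, with three parts of different weight. (a) is a real inconsistency: for a partly resolved flare the next ALT is 1 week or about 20 to 22 weeks away, depending on which sentence the site follows. That range assumes detection at Week 24, confirmation at about Week 25, decline seen at Weeks 26 to 28, visits on their nominal weeks and no unscheduled test. (b) is a mismatch between the resume bullet and both its own branch and the general rules. It does not show that drug restart is otherwise unchecked. (c) is a gap: neither of the two branches covers a subject who meets only the second trigger, but other rules still apply. How many subjects this affects cannot be derived from the documents, and nor can whether sites in fact differed. No endpoint, power or alpha figure changes.

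**What to change.** Reconcile the wording in three places:

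1. In the normal-bilirubin branch, reconcile the weekly-monitoring sentence with the decline bullet, so that one stated condition governs when ALT/AST have fallen but are not yet normal or at baseline.
2. In the raised-bilirubin/PT branch, reconcile the resume bullet with the weekly-monitoring sentence, the Week 8 consultation bullet and Sections 7.5 to 7.5.3, and say which parameters the resume condition refers to.
3. Make the branches cover both triggers, or refer explicitly to the rules that govern the remaining cases.

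The clinical thresholds and rules are for the sponsor's clinicians to choose; none is proposed here. The cost is a protocol clarification, with no new scheduled visits or staff.

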7.6. Special Situations Reports

7.6.1. Definitions of Special Situations

Special situation reports include reports of pregnancy; medication error, abuse, misuse, or overdose; lack of effect; adverse reactions in infants following exposure from breastfeeding; and adverse reactions associated with product complaints and occupational exposure.

Medication error is any unintentional error in the prescribing, dispensing, or administration of a medicinal product while in the control of the health care provider, subject, or consumer.

Abuse is defined as persistent or sporadic intentional excessive use of a medicinal product by a subject.

Misuse is defined as any intentional and inappropriate use of a medicinal product that is not in accordance with the protocol instructions or the local prescribing information.

An overdose is defined as an accidental or intentional administration of a quantity of a medicinal product given per administration or cumulatively which is above the maximum recommended dose as per protocol or in the product labelling (as it applies to the daily dose of the subject in question). In cases of a discrepancy in drug accountability, overdose will be established only when it is clear that the subject has taken the excess dose(s). Overdose cannot be established when the subject cannot account for the discrepancy except in cases in which the investigator has reason to suspect that the subject has taken the additional dose(s).

Product complaint is defined as complaints arising from potential deviations in the manufacture, packaging, or distribution of the medicinal product.

Lack of effect is defined as the failure of the expected or intended pharmacologic action or therapeutic effect as described in the pharmacology and/or indications section of the current product labeling.

Occupational exposure is defined as exposure to a medicinal product as a result of one's professional or non-professional occupation.

7.6.2. Instructions for Reporting Special Situations

7.6.2.1. Instructions for Reporting Pregnancies

The investigator should report pregnancies in female study subjects that are identified after initiation of study medication (i.e., Tenofovir DF) and throughout the study to the CRO or Gilead DSPH using the pregnancy report form within 24 hours of becoming aware of the pregnancy.

Refer to Section 7.3 and the CRF/eCRF completion guidelines for full instructions on the mechanism of pregnancy reporting.

The pregnancy itself is not considered an AE nor is an induced elective abortion to terminate a pregnancy without medical reasons.

Any premature termination of pregnancy (eg, a spontaneous abortion, an induced therapeutic abortion due to complications or other medical reasons) must be reported within 24 hours as an SAE. The underlying medical reason for this procedure should be recorded as the AE term.

A spontaneous abortion is always considered to be an SAE and will be reported as described in Sections 7.1.1 and 7.1.2. Furthermore, any SAE occurring as an adverse pregnancy outcome post study must be reported to Gilead DSPH.

The subject should receive appropriate monitoring and care until the conclusion of the pregnancy. The outcome should be reported to CRO [TBD] or Gilead DSPH using the pregnancy outcome report form. If the end of the pregnancy occurs after the study has been completed, the outcome should be reported directly to Gilead DSPH. Gilead DSPH contact information is as follows: Email: [contact] and [contact].

Refer to [Appendix 5](#) for Pregnancy Precautions, Definition for Female of Childbearing Potential, and Contraceptive Requirements.

